6 STUDY SUBJECTS

6.1 INCLUSION CRITERIA

A maximum of up to 64 patients will be enrolled in this prospective single-center single-arm study. Patients undergoing AF ablation (including paroxysmal and persistent AF) will be included in this study. Consistent with the current definitions, paroxysmal AF are episodes that will self-terminate in less than 24 hours. Persistent AF, is defined as ≥ 1 documented AF lasting >1 week in duration or lasting less than 7 days but requiring electrical or pharmacological cardioversion to sinus rhythm.

- Age >18 - Age < 80 yr
- Documentation of atrial fibrillation (AF)
- General anesthesia
- All patients must understand and adhere to the requirements of the study and be willing to comply with the post study follow-up requirements.

6.2 EXCLUSION CRITERIA

- Any reversible cause of AF (post-surgery, thyroid disorder, etc.)
- INR > 4.0 at the time of the procedure
- H/o of severe esophageal ulcers, strictures, varices, bleeding, laceration or perforation, esophagitis
- Severe GERD
- H/o esophageal surgery or any esophageal banding or cautery
- History of chest radiation
- Significant abnormality on Swallowing Impairment Score
- Mental impairment precluding signing consent or completing follow up
- Patients with any other significant uncontrolled or unstable medical condition
- Women who are known to be pregnant or have had a positive β -HCG test within 7 days prior to procedure
- Presence of left atrial thrombus

7 ANALYTICAL PLAN

7.1 SAMPLE SIZE CALCULATION

A single arm design is proposed. The primary endpoint will be the incidence of successfully moving the esophagus by a minimum of 1 cm from the ablation line for the ipsilateral PV pairs. We believe that 64 patients need to be enrolled in this single-arm study to achieve this endpoint. With 64 enrolled patients in this single-arm trial, if the true success rate is at least 90% then the statistical power will be 83% to detect such a performance by ruling out a poor success rate of $\leq 75\%$ using exact Binomial test at a two-sided 5% type-1 error rate. The test will reject the null hypothesis H_0 : Success Rate $\leq 75\%$ in favor of the alternative hypothesis H_1 : Success Rate $\geq 95\%$ if there are seven or fewer failures among 64 patients.

		Proportion Given H0 (P0)	Proportion Given H1 (P1)	Target Alpha	Actual Alpha	Reject H0 If Beta	$\leq R \mid \geq R$
Power	N	0.7500	0.9000	0.0500	0.0410	0.01679	33 47

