8 PATIENT ENROLLMENT AND WITHDRAWAL

Patients meeting the study inclusion criteria will be identified in the outpatient setting by one of the study staff.

The study will typically be described (including the risks and benefits) during the clinic visit. Consent will typically be obtained at the time of the initial assessment if it is clear that the patient truly understands the nature of the study. Alternatively, the patient will be allowed to take a copy of the consent form home to contemplate whether they would like to be enrolled in the study. Only patients who voluntarily provide consent will be included in this study. Consent will be obtained prior to undergoing the ablation procedure. Patients will be able to withdraw from the study at any point without compromising their medical care.

Since there is minimal additional follow-up beyond routine clinical care in this study, we expect to achieve > 95% rate of follow-up.

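### Section 7.1 takes its seven-failure rule and 83% power from a 54-patient design; at 64 patients that rule has 69% power and is stricter than the exact test the plan names

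*Combined protocol and SAP*

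**What the plan says.** Section 7.1 fixes the sample size at 64 ("We believe that 64 patients need to be enrolled in this single-arm study to achieve this endpoint"), and section 6.1 makes that number a ceiling ("A maximum of up to 64 patients will be enrolled in this prospective single-center single-arm study"). The power statement in 7.1 reads "With 64 enrolled patients in this single-arm trial, if the true success rate is at least 90% then the statistical power will be 83" per cent, against a null success rate of 75% or less, "using exact Binomial test at a two-sided 5% type-1 error rate". The decision rule follows: the null is rejected "if there are seven or fewer failures among 64 patients". That sentence writes the alternative as 95% or more, although the power statement uses 90%.

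The table under the paragraph gives P0 = 0.75, P1 = 0.90, target alpha 0.05, actual alpha 0.0410, beta 0.01679, and rejection at 33 or fewer or 47 or more successes. In the copy reviewed, no value for N or power can be read in the table; this may be a loss in text extraction, and nothing below depends on it.

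Section 7.1 mentions no allowance for dropout. Section 8 says "we expect to achieve > 95% rate of follow-up".

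**The concern.** Among 64 patients, seven failures means 57 successes, but the table's upper bound is 47. Those two numbers agree only if N = 47 + 7 = 54. This suggests that the software output was produced for 54 patients and that its cut-off and power were then attached to 64.

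The paragraph is the only specification of the trial's one confirmatory test. If the count rule and the named test give different verdicts for the same data, the choice between them could be made after the result is known. The stated power would also not be the power of the stated rule.

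**Working it through.** **Inputs.** From 7.1: N = 64, p0 = 0.75, p1 = 0.90, exact binomial test at two-sided 5%, rejection at seven or fewer failures; from its table, bounds 33 and 47, actual alpha 0.0410, beta 0.01679. Let X be the number of successes, X ~ Binomial(N, p).

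**Step 1: reproduce the plan's figures.** For bounds 33 and 47, alpha = P(X ≤ 33 | 0.75) + P(X ≥ 47 | 0.75) and beta = 1 − P(X ≥ 47 | 0.90).

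| N | alpha | beta |
|---|---|---|
| 52 | 0.0478 | 0.4208 |
| 53 | 0.0387 | 0.2769 |
| **54** | **0.0410** | **0.1679** |
| 55 | 0.0556 | 0.0944 |
| 56 | 0.0840 | 0.0494 |

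Of all N from 40 to 99, only 54 gives 0.0410 (0.0169 lower + 0.0241 upper). Power there is 1 − 0.1679 = 83.2%, and 54 − 47 = 7 failures. The printed beta has the right digits with the decimal point one place out: 0.01679 would mean 98.3% power.

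**Step 2: the written rule at N = 64.** Seven or fewer failures means X ≥ 57.
- P(X ≥ 57 | 0.75) = 0.0043
- P(X ≥ 57 | 0.90) = 0.692
- Risk of missing a true 90% rate: 1 − 0.692 = 0.308, against 1 − 0.83 = 0.17 as claimed

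**Step 3: the named test at N = 64**, with at most 0.025 in each tail.
- P(X ≥ 55 | 0.75) = 0.02524, just above 0.025
- P(X ≥ 56 | 0.75) = 0.0111, so the upper cut-off is 56 successes (64 − 56 = 8 failures)
- P(X ≤ 40 | 0.75) = 0.0181, so actual two-sided alpha = 0.0111 + 0.0181 = 0.0292
- P(X ≥ 56 | 0.90) = 0.8134, so power is 81.3% and beta 0.1866

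**Step 4: where the two rules part.** With exactly eight failures the observed rate is 56/64 = 87.5%.
- Two-sided p = 2 × 0.0111 = 0.022 by doubling, or 0.020 by the minimum-likelihood method
- Clopper-Pearson 95% lower limit: 76.8%, above 75%
- The exact test rejects the null; the count rule does not
- Probability of this outcome at a true rate of 90%: 0.8134 − 0.6922 = 0.121

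The two-sided method also matters. With nine failures (55/64), doubling gives 2 × 0.02524 = 0.0505 and the minimum-likelihood method gives 0.043. Under the latter the test also rejects at nine failures, and the rules disagree with probability 0.8972 − 0.6922 = 0.205 at a true rate of 90%. The table does not settle which method was meant: at N = 54, 47 successes is the upper cut-off under both.

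**The case against.** **64 is 54 evaluable patients plus an allowance for loss.** Under an assumed 15% loss, 54/0.85 = 63.5, which rounds up to 64. But 7.1 states no inflation and writes the rule for 64 patients. The distance is measured during the procedure (Appendix 2, data collection), so later loss to follow-up should hardly reduce the denominator. Patients could still drop out before ablation, or be excluded from deviation for a diverticulum; the plan gives no rate for either. The follow-up figure in section 8 therefore sets no firm floor on evaluable patients. As an illustration only, 95% of 64 is 60.8; with 61 patients the seven-failure rule has 73.7% power, still short of 83%.

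**83% could come from 64 after all.** A continuity-corrected normal approximation at N = 64 does give 83.2%, so the power figure alone does not prove a 54-patient origin. The plan names an exact test, however, and the bounds with alpha 0.0410 fit only 54.

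**The practical harm is limited.** Much of this stands. The seven-failure rule is conservative, so it cannot raise the false-success rate. The named test at N = 64 has power within two points of the claim. On the equal-tailed reading the rules differ at one result only. At a true rate of 95% the seven-failure rule has 98.6% power, and the disagreement has probability of about 1% (0.9956 − 0.9858). But the plan claims its power at 90%.

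**Applying the table's bound of 47 to 64 patients is not a realistic reading.** This is fair. It would reject a true 75% rate 67% of the time, but the table may originally have shown N = 54, and the text gives its own count. The conclusion does not rest on that figure.

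**Conclusion.** The concern holds. The cut-off, bounds and actual alpha in 7.1 belong to 54 patients, and the text applies the cut-off and the power to 64. As written, the decision rule has 69.2% power at a true rate of 90%, not 83%. It also contradicts the named test at eight failures, which has probability 12.1% at that rate. This must be corrected because it concerns the only confirmatory threshold and can reverse the verdict.

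The 81.3% and the eight-failure cut-off assume 64 evaluable patients and an equal-tailed exact test; the minimum-likelihood method would move the cut-off to nine failures. That the 64 came from 54 plus dropout is conjecture. The sample size is adequate and type I error is protected; the fault lies in the rule and the figures attached to it.

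**What to change.** In 7.1, replace the rule and the table row with the N = 64 values: P0 = 0.75, P1 = 0.90, target alpha 0.05, actual alpha 0.0292, beta 0.1866, lower bound 40, upper bound 56, success declared with 56 or more successes (eight or fewer failures), power 81.3%. In the same edit:

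- Name the two-sided exact method, for example equal-tailed with the Clopper-Pearson interval.
- Change the alternative hypothesis from 95% to 90%, so that it matches the power statement and the table.
- State that if the evaluable number is not 64, the cut-off is recomputed from the same exact test. With 61 patients, for instance, it would be 53 or more successes, with 84.8% power.
- If 54 evaluable patients was the intended design, say so, state the assumed loss, and apply the seven-failure rule to 54 only.

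The cost is a wording and table correction. No patients are added, and the stated power falls from 83% to 81%. The correction should be made before any primary endpoint results are reviewed.

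### Section 7.1 does not give one consistent decision rule at N=64: the printed seven-failure cut-off, the named exact test and the table disagree, and the printed cut-off has 69.2% power, not 83%

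*Combined protocol and SAP*

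**What the plan says.** All of the following is in Section 7.1 of the combined protocol and SAP.

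- Sample size: "With 64 enrolled patients in this single-arm trial".
- Power: "if the true success rate is at least 90% then the statistical power will be 83" percent.
- Null: "ruling out a poor success rate of $\leq 75\%$ using exact Binomial test".
- Error rate: "using exact Binomial test at a two-sided 5% type-1 error rate".
- Decision rule: "The test will reject the null hypothesis H_0 : Success Rate $\leq 75\%$ in favor of the alternative hypothesis", "if there are seven or fewer failures among 64 patients".
- Table row: "0.7500 0.9000 0.0500 0.0410 0.01679 33 47". Read against its column heads, this is P0, P1, target alpha, actual alpha, beta, and a rejection region of 33 or fewer or 47 or more successes. The power and N entries of the row are not readable in the text available to me.

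The section does not say how the two-sided exact p-value is formed.

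**The concern.** The success criterion appears in three forms: a named test, a count of failures, and a tabulated region. They should give the same answer for every possible result in 64 patients, and they do not.

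This is the only confirmatory decision in an open, single-arm, single-center study. The success count is visible as it accumulates. If the count and the named test disagree near the boundary, the reading could be settled after the result is known. The power claim that supports the sample size would also not belong to the rule that is printed.

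**Working it through.** **Inputs (Section 7.1).** p0 = 0.75, p1 = 0.90, N = 64, exact binomial, two-sided 5%. Printed rule: at most 7 failures, so at least 64 − 7 = 57 successes. Table: region 33 | 47, actual alpha 0.0410, beta 0.01679.

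**Formulas.** Upper-tail alpha = P(X ≥ c | N, 0.75). Power = P(X ≥ c | N, 0.90). Two-tailed alpha adds P(X ≤ d | N, 0.75), where d is the lower limit of the region.

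**Step 1: reproduce the plan's figures.** Taking the region 33 | 47 as given and searching N from 47 to 69, only N = 54 returns the printed alpha:

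- P(X ≤ 33 | 54, 0.75) = 0.0169
- P(X ≥ 47 | 54, 0.75) = 0.0241
- sum = 0.0410, as printed
- P(X ≥ 47 | 54, 0.90) = 0.832, so power is 83.2% and beta is 0.1679 (printed as 0.01679, which looks like a slipped decimal)
- 54 − 47 = 7 failures, as in the decision sentence

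The neighbouring sizes give 0.0387 (N = 53) and 0.0556 (N = 55). At N = 64 the same region would have alpha 0.674. So the table, the 83% and the seven failures all fit N = 54, and none of them fits N = 64.

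**Step 2: candidate cut-offs at N = 64.**

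| Successes (failures) | Upper-tail alpha | Doubled p | Probability-ordering p | Clopper-Pearson 95% lower limit | Power at 90% |
|---|---|---|---|---|---|
| 55 (9) | 0.0252 | 0.0505 | 0.0433 | 74.98% | 89.7% |
| 56 (8) | 0.0111 | 0.0223 | 0.0202 | 76.85% | 81.3% |
| 57 (7) | 0.0043 | 0.0086 | 0.0086 | 78.75% | 69.2% |

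For 55/64 the probability-ordering p-value is 0.0252 + P(X ≤ 40) = 0.0252 + 0.0181 = 0.0433. The equal-tailed test compares 0.0252 with 0.025 and misses by 0.0002.

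**Step 3: compare the rules.**

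- 57 or more: all readings reject.
- 56: the named test rejects under either exact method; the printed rule does not.
- 55: the named test rejects by probability ordering and does not reject with equal tails or Clopper-Pearson; the printed rule does not reject.
- 54 or fewer: no reading rejects (upper tail 0.0511 at 54).

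**Step 4: the relevant error.** Under a null of at most 75%, few successes support the null, so only the upper tail is a type-1 error. In the table's own design that is 0.0241, not 0.0410.

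**Step 5: fewer than 64 analysed.** The printed count is defined only for 64. The one-sided 2.5% exact test rejects at 52/60, 53/61, 54/62 and 55/63, which is eight failures each time, with power at 90% of 85.8%, 84.8%, 83.7% and 82.5%.

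**The case against.** **The printed rule already decides 55/64.** It does: nine failures exceed seven, so the null is not rejected. A reader might infer that 55/64 passes or fails according to whether the test is taken as one-sided or two-sided. The documents do not support that. Section 7.1 says two-sided and gives a count. The split at 55 also arises between two methods that are both two-sided 5%; one-sided 5% is never offered. What remains is that the count is not the cut-off of the test named beside it, so 55 and 56 can be argued from the same paragraph.

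**Pairing a directional claim with two-sided 5% is conventional.** This stands. It is ordinary shorthand for 2.5% in the relevant tail, and the lower region looks like routine output for a two-sided power calculation. A reader might infer an inflated type-1 error from the 0.0410. That does not follow: the upper tail is 0.0241 at N = 54 and 0.0043 for the printed rule at N = 64. At N = 54 the upper cut-off is 47 whether the test is one-sided 5%, one-sided 2.5%, equal-tailed or probability-ordered, because P(X ≥ 46) = 0.0525. The trouble appears only when the calculation is carried to 64.

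**Perhaps 64 is 54 evaluable patients inflated for loss.** The arithmetic allows it: 54 / 0.85 = 63.5, which rounds up to 64. But Section 7.1 states no inflation, Section 8 expects more than 95% follow-up, and the decision sentence applies seven failures to 64. This remains a guess.

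**Conclusion.** The point holds as an inconsistency in the decision rule. At N = 64 the printed cut-off is one patient stricter than the named test with equal tails, and two stricter than the same test by probability ordering. Its power is 69.2% against the stated 83%, a shortfall of about 14 points. The error is conservative, so false-positive control is not at risk.

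Nor does it show that 64 patients are too few: the named test with equal tails gives 81.3% at that size.

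These figures assume a true rate of 90%, independent patients and all 64 analysed. The hypothesis sentence instead writes the alternative as "Success Rate $\geq 95" percent, which conflicts with the 90% used for power and in the table. It changes no cut-off, but it should be reconciled in the same edit. The N = 54 origin is inferred from the arithmetic and is not stated in the plan.

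**What to change.** In Section 7.1:

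1. State the test as a one-sided exact binomial test of a success rate of at most 75% at 2.5%, equivalent to the lower limit of the two-sided Clopper-Pearson 95% interval exceeding 75%.
2. Delete the lower rejection region.
3. Replace both the seven-failure sentence and the table row with the N = 64 figures: reject at 56 or more successes (8 or fewer failures), actual one-sided alpha 0.011, power 81.3% at a true 90%. Changing one and leaving the other would create a new contradiction.
4. Say that the same named test applies if fewer than 64 are analysed.
5. Give the alternative as one value throughout.

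**Cost.** Wording and one table row, with no extra patients or data. Stated power falls from 83% to 81.3%, and the printed criterion is relaxed from seven failures to eight. The change should be declared openly, ideally before outcome data are reviewed. If the sponsor prefers to keep seven failures in 64, it should restate power as 69.2% and upper-tail alpha as 0.0043.

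### Section 7.1 names a success rate of at least 95% as the alternative, but its power is worked at 90% and a rejection supports only a rate above 75%

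*Combined protocol and SAP*

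**What the plan says.** All of the text on the primary test is in Section 7.1 (Sample size calculation). It gives the following:

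- **Sample size:** "With 64 enrolled patients in this single-arm trial".
- **Null:** the aim is described as "ruling out a poor success rate of $\leq 75"%.
- **Rate used for power:** "if the true success rate is at least 90% then the statistical power will be 83"%.
- **Test:** "using exact Binomial test at a two-sided 5% type-1 error rate".
- **Decision rule:** the null is rejected in favor of the "alternative hypothesis H_1 : Success Rate $\geq 95\%$ if there are seven or fewer failures among 64 patients".
- **Software table:** the legible row reads "0.7500 0.9000 0.0500 0.0410 0.01679 33 47". By the column heads these are P0 = 0.75, P1 = 0.90, target alpha 0.05, actual alpha 0.0410, beta, and the lower and upper rejection limits.

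Section 5.1 defines the primary endpoint as an incidence and sets no target rate. The only other use of 95% as a rate is the expected follow-up in Section 8. Section 7 has no plan for estimation or confidence intervals.

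**The concern.** The test has one null but two alternatives, 90% and 95%, within a few lines. The higher figure stands in the sentence that says what a rejection favors.

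A test against 75% can only show that the rate is above 75%. How far above is a matter for the estimate and its interval, and Section 7 plans neither. The decision sentence is therefore the plan's most explicit statement of what a positive primary result means, and it carries a figure that the test cannot support. At stake is the strength of the claim about the device, not whether the trial is declared positive.

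**Working it through.** **Inputs, all from Section 7.1.** N = 64; p0 = 0.75; rate used for power p1 = 0.90 (text and table); H1 in the decision rule 0.95 or more; reject with at most 7 failures; exact binomial, two-sided 5%; stated power 83%; table alpha 0.0410 with limits 33 and 47. X is the number of successes, X ~ Bin(N, p).

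**1. Which rate does the 83% belong to?** First, reproduce the plan's own figures. The table's limits (reject if X ≤ 33 or X ≥ 47) give its alpha at N = 54:

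- Alpha = P(X ≤ 33 | 54, 0.75) + P(X ≥ 47 | 54, 0.75) = 0.0169 + 0.0241 = 0.0410.
- Power at 0.90 = 83.2%, so beta = 1 − 0.832 = 0.168. The printed beta has the same digits with the decimal point one place further left.
- Failures allowed = 54 − 47 = 7.
- Power of the same rule at 0.95 = 99.5%.

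So the 83% is a calculation at 90%, made for 54 patients. At N = 64 the limits 33 and 47 would give alpha of about 0.67, so the table cannot describe 64 patients.

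**2. The rule as written, 64 patients.** At most 7 failures means X ≥ 64 − 7 = 57.

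| True rate | P(X ≥ 57), N = 64 |
|---|---|
| 0.75 | 0.0043 |
| 0.90 | 69.2% |
| 0.95 | 98.6% |

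Neither sample size gives 83% at a true rate of 95%. The drop to 69.2% at 90% comes from pairing a seven-failure rule with 64 patients. That is a separate error and is not caused by the 95% label.

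**3. What a rejection supports.** Exact (Clopper-Pearson) two-sided 95% intervals:

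| Result | Observed rate | Interval |
|---|---|---|
| 57/64 (weakest that qualifies) | 89.1% | 78.8% to 95.5% |
| 64/64 (best possible) | 100% | lower limit 0.025^(1/64) = 94.4% |

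Every qualifying result excludes 75%. None has a two-sided lower limit that reaches 95%.

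**4. Does the 95% enter the decision?** No. The cut-off and alpha are set by N and p0 = 0.75, and power by those and p1 = 0.90. Replacing 95% with any other label leaves all three as they are.

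**The case against.** The strongest reply is that this is a one-number slip with no operating effect. The section gives 90% twice, no other section sets a 95% success target, and the sentence before the decision rule states the inference correctly as excluding 75%. The decision is the same with or without the correction. All of that stands, and it limits the weight of the point.

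A reader might infer more than the documents support in four ways:

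- **That the trial plans to announce a success rate of at least 95%.** No section sets a reporting rule of that kind. Section 4 aims to confirm safety and feasibility. The risk of overstatement lies in the wording of the hypothesis, not in a declared intention.
- **That a qualifying result would contradict 95%.** Under the written rule the weakest qualifying interval, 78.8% to 95.5%, still includes 95%. The lower tail P(X ≤ 57 | 64, 0.95) is 4.0%, which is borderline, and at 58/64 it is 10.0%. The interval excludes 95% only at 56/64 (76.8% to 94.4%), a result that the written rule does not accept. Nor does it tell against the rule that 89.1% lies below H1, since it also lies below the 90% design value.
- **That no result in 64 patients could ever show 95%.** This holds for the two-sided 95% interval, which matches the plan's two-sided test. A one-sided 95% bound at 64/64 is 0.05^(1/64) = 95.4%.
- **That the gap between H0 and H1 is itself a fault.** Leaving a zone between the null and the design alternative is a common single-arm convention.

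The reply does not dispose of two things. The figure is wrong in the statement of the primary hypothesis, and changing 95% to 90% would make the text consistent but would still let a rejection be read as showing a rate that the test does not establish.

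**Conclusion.** The inconsistency is real and of moderate weight. Section 7.1 states the alternative as at least 95%, while its power sentence and table use 90% and nothing in the section was computed for 95%. A rejection supports a success rate above 75% and no more.

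It is an error in the stated hypothesis and conclusion only. It does not invalidate the test or change who counts as a success, and it is not the cause of the mismatch between 54 and 64 patients in the same section.

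The conclusion assumes that the 95% is printed as the sponsor wrote it; it stands in a complete, readable sentence. The interval figures assume exact two-sided 95% limits, the choice that matches the stated test, and all 64 patients evaluable.

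**What to change.** Rewrite the decision sentence in Section 7.1 as: H0, success rate at most 75%; H1, success rate above 75%; 90% is the design value at which power is calculated. Add that a rejection will be reported as a success rate above 75%, with the observed rate and its exact two-sided 95% confidence interval.

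Make this change in the same revision that brings the sample size, cut-off, alpha and power to one consistent N. Correcting those figures alone would leave the 95% standing.

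The cost is one line of text, with no added patients, data or procedures. The downside for the sponsor is a less favorable permitted claim.

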7.2 STOPPING CRITERIA

STOPPING CRITERIA

We propose as a stopping criterion the occurrence of 1 case or more of esophageal laceration based on the finding of the Barium Swallow.

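### The rule of seven or fewer failures among 64 does not match the exact test named in Section 7.1, and no rule is stated if the trial ends below 64

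*Combined protocol and SAP*

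**What the plan says.** Section 7.1 names the test and gives a power figure. It speaks of "ruling out a poor success rate of $\leq 75\%$ using exact Binomial test" at a two-sided 5% level, and says that "if the true success rate is at least 90% then the statistical power will be 83" per cent. The sample is described as "With 64 enrolled patients in this single-arm trial", and the null is rejected "if there are seven or fewer failures among 64 patients". The software table below the text prints a null of 0.75, an alternative of 0.90, actual alpha 0.0410, a beta of 0.01679, and critical values 33 and 47. The power and N entries of that row are not legible in the text available for this review. The hypothesis sentence gives the alternative as 95%.

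Three other provisions bear on how many patients will be analysed:

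- Section 6.1: "A maximum of up to 64 patients will be enrolled in this prospective single-center single-arm study".
- Section 7.2 makes a "stopping criterion the occurrence of 1 case or more of esophageal laceration", judged on the barium swallow. It does not say how the primary endpoint is analysed after a stop.
- Section 8: "Consent will typically be obtained at the time of the initial assessment", whereas Section 6.2 has at least one exclusion judged later: "INR > 4.0 at the time of the procedure". The Work Flow in Appendix 2 also withholds deviation when contrast shows a diverticulum, and lists that step after device insertion.

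No section defines the moment of enrolment or the primary analysis set. None says how patients without deviation or without a measurement are counted.

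**The concern.** A failure count is a cut-off for one sample size only. If the printed count was derived for a different number from the 64 planned, the stated error rate and power describe a test that will not be run. If the trial then ends below 64, the count has no defined meaning. The analyst would have to choose among declaring no result, carrying seven failures down to the smaller number, or recomputing the cut-off, and would choose with the data in hand. The first option discards usable evidence on feasibility. The second becomes too lenient once the number is small enough. At stake is whether the primary conclusion can be defended as pre-specified.

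**Working it through.** **Inputs.** From Section 7.1: null 0.75, power evaluated at 0.90, two-sided 5% (0.025 in the upper tail), N = 64, at most 7 failures. From Section 4, preliminary data: over 200 patients treated, no complications reported. The laceration rate q is not in the documents, so it is assumed over 0.1% to 1.5%. The top of that range is the one-sided 95% upper limit for 0 of 200: 1 − 0.05^(1/200) = 1.5%.

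**1. The plan's own figures.** Let X be the number of successes.

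- At N = 54 with critical values 33 and 47: P(X ≥ 47 | 0.75) = 0.0241 and P(X ≤ 33 | 0.75) = 0.0169, total 0.0410. Power at 0.90 is 0.832, so beta is 0.168. This matches the printed alpha, the critical values and the 83%. It also matches the printed beta if that is read as 0.1679. Since 54 − 47 = 7, the seven-failure limit comes from here.
- At N = 64, 47 successes would be 47/64 = 73%, below the null, so 47 cannot be an upper critical value for 64.

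**2. The rule at 64.**

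| Failures allowed | Upper-tail alpha at 75% | Power at 90% |
|---|---|---|
| 7 (stated) | 0.0043 | 69.2% |
| 8 | 0.0111 | 81.3% |
| 9 | 0.0252 | 89.7% |

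Nine just exceeds 0.025, so the named test allows eight. Exact 95% lower limits agree: 76.8% for 56/64, and 74.98% for 55/64. Using the 95% alternative does not rescue the 83%, because power with seven failures is then 98.6%.

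**3. Chance of reaching 64 without a laceration,** (1 − q)^64: 94%, 73%, 53% and 38% at q = 0.1%, 0.5%, 1% and 1.5%. The chance of a stop at or before patient 53, 1 − (1 − q)^53, is 5%, 23%, 41% and 55%.

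**4. Seven failures carried down to n,** P(at most 7 failures | n, 0.25):

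| n | 63 | 60 | 54 | 53 | 50 | 40 | 30 |
|---|---|---|---|---|---|---|---|
| Upper-tail alpha | 0.5% | 0.9% | 2.4% | 2.8% | 4.5% | 18% | 51% |

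**5. Exact test recomputed at n** (upper tail ≤ 0.025): at most 7 failures at 54, 6 at 50, 4 at 40 and 2 at 30, with power at 90% of 83.2%, 77.0%, 62.9% and 41.1%. Below 13 patients no result can reject, since 0.75^12 = 0.032 and 0.75^13 = 0.024.

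**6. Overall chance of a positive result at 90% success,** taking laceration as independent of deviation success and the triggering patient as the last one treated. The last column sums, over stopping times, the probability of stopping at n times the exact-test power at n.

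| q | Complete, ≤7 failures | Complete, ≤8 failures | Exact test at n reached |
|---|---|---|---|
| 0.1% | 0.938 × 0.692 = 65% | 0.938 × 0.813 = 76% | 79% |
| 1% | 0.526 × 0.692 = 36% | 0.526 × 0.813 = 43% | 62% |

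The first step in each row comes from correcting the cut-off. Only the second comes from using trials that stop early.

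**7. Unevaluable patients counted as failures out of 64,** stated rule, P(X ≥ 57 | 64 − m, 0.90): 69.2%, 55.6%, 40.4% and 25.8% for m = 0, 1, 2 and 3.

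**The case against.** The strongest reply is that the plan does have a valid test. Section 7.1 names an exact binomial test against 75%, and that test can be recomputed at any n; the count is only its cut-off at the planned size. This is right, and it rules out the reading that no valid rule exists below 64. What remains is that the only rejection criterion written down is the count, that the count disagrees with the test, and that nothing says the test is to be recomputed.

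Four other inferences are tempting but not supported.

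- *The 83% holds provided all 64 are treated.* It does not: the stated rule gives 69.2% at 64. Making 83% conditional on reaching 64 would leave a wrong figure in place.
- *Any shortfall makes seven failures lenient.* From 54 to 63 patients, upper-tail error stays within 2.5%. A few procedure-day exclusions cause no inflation; a stop at 53 or fewer does. Nor does the plan propose using seven at a smaller n.
- *Patients count as enrolled before procedure-day exclusions.* That is inferred from the timing of consent. Enrolment is undefined, and the Work Flow has staff confirm eligibility before the device is inserted.
- *The 64 is 54 evaluable patients inflated for losses.* The plan does not say so, and 54/64 = 84% does not sit with the more than 95% follow-up expected in Section 8.

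It is also fair to say that a trial stopped for laceration has delivered its safety finding, that its deviation rate can still be reported with an interval, and that a stop is not shown to be likely. At a rate of 0.1%, 94% of trials reach 64. Finally, seven failures at 64 is conservative for type I error. A sponsor may choose a stricter bar, but not together with a claim of 83% power.

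**Conclusion.** The point holds in two parts. The first needs no outside assumption: the cut-off, alpha and power printed in Section 7.1 belong to 54 patients. At 64, the stated rule spends 0.4% of the 2.5% upper-tail allowance and has 69.2% power at 90% success, about 14 points below the 83% claimed. The named test gives eight failures and 81.3%.

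The second is an omission: the plan states no decision for fewer than 64 patients, although its own cap and stopping criterion allow that outcome. How often it arises depends on a laceration rate that is assumed here, and the overall probabilities also assume independence from deviation success. Under that independence, applying the exact test at the number reached costs power but does not inflate type I error, because the test is held at 2.5% at every n. If failed or difficult deviations also carry more lacerations, the overall figures would change.

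This should be corrected before results are seen. It does not undermine the design.

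**What to change.** Replace the count in Section 7.1 with a rule of this form:

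> Reject H0 if the lower limit of the exact two-sided 95% confidence interval for the success rate exceeds 75% (upper-tail exact p ≤ 0.025), at the number of patients in whom DV8 insertion was attempted, whether or not 64 is reached.

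Then:

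- State that this means at most eight failures at 64.
- Restate power as 81% at 90% success, conditional on 64 evaluable patients, and replace the table with one computed for 64. Give one alternative, 90% or 95%, throughout.
- In Section 6.1, count the 64 as attempted insertions, so that patients excluded beforehand do not use up places.
- State how patients excluded from deviation for a diverticulum after insertion, and patients without a measurement, enter the numerator and denominator.
- Leave the stopping criterion in Section 7.2 unchanged.

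The cost is a few sentences and two visible changes that should be disclosed: the stated power falls from 83% to about 81%, and the failures allowed at 64 rise from seven to eight.
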